## STUDY SYNOPSIS

*Please provide a brief summary of the information provided in the Protocol.*

Title:	Reducing the frequency of Autoimmune adverse events in the treatment of Multiple sclerosis with alemtuzumab using B-cell depletion (RAMBLE)
Short Title:	RAMBLE Trial
Study Sites:	Gold Coast University Hospital Royal Brisbane and Women's Hospital Mater Hospital Princess Alexandra Hospital Sunshine Coast University Hospital Townsville Hospital and Health Service
Study Aims/Objectives/Hypothesis:	To reduce the occurrence of autoimmune adverse events from the treatment of multiple sclerosis (MS) with alemtuzumab through the subsequent targeted use of rituximab. The hypothesis to be tested is that rituximab therapy following alemtuzumab treatment for MS will reduce the frequency of autoimmune adverse events.
Study Design:	This is a multicentre, randomised, double-blind, placebo-controlled Phase II clinical trial.
Study Outcome Measures:	The occurrence of autoimmune disease adverse events, in particular autoimmune thyroid disease, idiopathic thrombocytopenia and anti-GBM renal disease.
Study Population:	People with relapsing remitting MS undergoing therapy with alemtuzumab for the treatment of their disease.
Number of participants:	80
Translation to Clinical Practice:	If this strategy proves to be safe and is effective in preventing or significantly reducing the frequency of autoimmune adverse events in the treatment of MS with alemtuzumab, then this approach could be adopted immediately in a large number of pwMS with an immediate reduction in co-morbidity.
Key Ethical and Safety Considerations:	Is the consecutive administration of alemtuzumab and rituximab safe?

---

## Glossary of Abbreviations, Terms, and Acronyms

Abbreviation, Term, Acronym	Definition (using lay language)
AAN	American Academy of Neurology
ANZAN	Australian and New Zealand Association of Neurologists
BSA	Body Surface Area
CARE-MS	Comparison of Alemtuzumab and Rebif® Efficacy in Multiple Sclerosis
CNS	Central Nervous System
CONSORT	Consolidated Standard of Reporting Trials
CRO	Contract Research Organisation
CTN	Clinical Trial Notification
ECTRIMS	European Committee for Treatment and Research in Multiple Sclerosis
EDSS	Expanded disability status scale
eCRF	Electronic Case Report Form
EUC	Electrolytes Urea and Creatinine
FBC	Full Blood Count
HADS	Hospital Anxiety and Depression Scale
βhCG	Beta-human Chorionic Gonadotropin
ICH-GCP	International Conference on Harmonization – Good Clinical Practice
ieMR	Integrated Electronic Medical Record
HREC	Human Research Ethics Committee
HSV2	Herpes Simplex Virus Type 2
LFT	Liver Function Tests
LTFU	Loss to Follow Up
MedDRA	Medical Dictionary for Regulatory Activities
MRFF	Medical Research Future Fund

MRI	Magnetic Resonance Imaging
MS	Multiple sclerosis
MSIS-29	Multiple Sclerosis Impact Scale-29
MSRA	Multiple Sclerosis Research Australia
NHMRC	National Health and Medical Research Council
od	Omne in Die (Once Daily)
PBS	Pharmaceutical Benefits Scheme
PICF	Patient Information and Consent Form
PIDN	Patient Identification Number
PO	Per Oral (Taken Orally)
pwMS	People with Multiple Sclerosis
QML	Queensland Medical Laboratories
RRMS	Relapse Remitting Multiple Sclerosis
SAE	Serious Adverse Event
TFT	Thyroid Function Test
TSH	Thyroid Stimulating Hormone
UACR	Urinary Albumin/Creatinine Ratio

---

## 1. Background

Multiple sclerosis (MS) is the commonest cause of neurological disability in young adults, and particularly affects women. Left untreated, MS causes marked difficulty walking or inability to walk in more than half after 20-30 years. This dire prognosis has been radically altered by the advent of a variety of effective therapies, including three highly effective infusion therapies.

Alemtuzumab is a highly effective therapy for the treatment of MS. In pivotal phase III clinical trials (CARE-MS I and II) alemtuzumab reduced the risk of relapse by 51-55% (Class I evidence) and sustained disability by 30-42% (Class I evidence) when compared against a proven, active-comparator, therapy in the form of interferon beta 1a. This novel therapy is administered as two courses, the first over 5 days and the second course over 3 days, 12 months later. In the majority (53%) of people with MS (pwMS) treated with alemtuzumab no further therapy was required over 8 years of follow up. The annual cost of alemtuzumab is similar to other highly effective therapies for MS (around \$30,000 per year). Because only two years of therapy is required in most pwMS and rarely are more than three courses given, the recurring costs of this therapy are considerably less than other similarly efficacious therapies (natalizumab and ocrelizumab) which have to be administered on a recurring basis seemingly indefinitely. However, the use of alemtuzumab as a therapy in pwMS has been relatively limited and this is in large part because of a significant risk of autoimmune adverse events. Autoimmune thyroid disease occurs in approximately one-third of patients and idiopathic thrombocytopenia (2%) and anti-GBM renal disease (0.5%) are seen less commonly, together with a variety of other occasional autoimmune diseases that have been described. It has been noted that this phenomenon is specifically seen in MS and does not occur as frequently in other indications for this therapy.

Alemtuzumab is a monoclonal antibody against CD52 which is a cell surface marker of lymphocytes of unknown function. The antibody is lytic to lymphocytes and causes a profound temporary lymphopenia following intravenous administration. Bone marrow derived lymphocytes begin to re-emerge almost immediately and by 3 months are up to 70% of pre-treatment levels. One of the features of this lymphocyte repopulation is that B-cells re-emerge faster than T-cells. It has therefore been postulated that the extra-thymic self-tolerisation of B-cells in the absence of regulatory T-cells might explain the frequent emergence of autoimmune disease following treatment with alemtuzumab. It has further been suggested that one strategy to ameliorate the emergence of autoimmunity following alemtuzumab, B-cell depleting agents could be used to quell their early re-emergence. B-cell depleting agents have been used to successfully treat autoimmune disease following alemtuzumab.

A recent phase I, open label, single arm clinical trial of rituximab therapy administered whenever B-cell counts reached 50% of baseline levels following treatment of MS with alemtuzumab demonstrated that this approach is safe and potentially completely effective in mitigating the risk of autoimmunity (Class V evidence).

In view of this preliminary data, it is proposed that a phase II, placebo-controlled clinical trial be undertaken with the aim of assessing the effectiveness of B-cell depletion in mitigating the risk of autoimmune disease following treatment with alemtuzumab in pwMS.

---

## 2. Study Objectives

### a. Research Question and Aims/objectives

- *Primary Objective*
  - *To demonstrate a reduction or complete abrogation of the occurrence of autoimmune disease with administration of rituximab following treatment with alemtuzumab for MS.*
- *Secondary Objectives*
  - *To assess the safety and efficacy (MS disease activity related) of this therapeutic approach.*
  - *To assess the profile of the immune repertoire of T and B-cells that re-emerge with this therapeutic approach.*
  -

### b. Hypotheses

- *The following hypotheses will be tested:*
  - *1) Consecutive administration of alemtuzumab and rituximab is associated with a lower risk of autoimmune adverse events than when alemtuzumab is administered with placebo.*
  - *2) Consecutive administration of alemtuzumab and rituximab is associated with similar efficacy in MS disease control when compared to the administration of alemtuzumab with placebo.*
  - *3) Consecutive administration of alemtuzumab and rituximab is safe – adverse events will be no more common than when alemtuzumab is administered with placebo.*
  - *4) The early re-emergence of B-cells following alemtuzumab therapy is suppressed by the administration of rituximab when compared to placebo.*

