## **I. Data Analysis and Statistical Considerations**

- *The primary outcome measure for this study will be frequency of autoimmune adverse events. Because the duration of follow up will not be uniform for all participants and in order to make the maximal use of data the frequency of autoimmune adverse events will be modelled using a Cox Proportional Hazards time to event analysis (with onset of autoimmune adverse event as the event of interest). Although randomisation will be stratified for clinical site and sex, these factors as well as age and disease severity (MSSS) will be included in the model. Analysis will be performed on an intention-to-treat basis.*
- *Secondary outcome measures will be analysed as follows:*
  - *Other adverse events (MedDRA terms) will be compared using frequencies and chi-squared statistics.*

- 
- *Efficacy in terms of MS outcomes will be analysed using time to event analysis (Cox Proportional Hazards method) for annualized relapse rate and sustained disability progression (6 months), including the factors listed above for the primary outcome analysis in the model.*
  - *Other secondary outcomes (e.g. change in EDSS, new T2 and Gd-enhancing MR imaging lesions) at 1 and 2 years will be assessed using linear regression analysis provided assumptions are met (in which case non-parametric methods will be used).*
  - *Any effect of laboratory measures (lymphocyte subsets,) and baseline characteristics will be explored using regression analysis.*
  - *All statistical analyses will be conducted using STATA® v16 software (StatCorp®, US). The primary outcome of this trial will be met if the hazard ratio of autoimmune adverse events in the treatment (rituximab) arm is significantly lower than that seen in the placebo arm. The study is unlikely to have sufficient power to identify any significant differences in the frequency of other adverse events or MS disease outcome measures, but these will be looked at carefully to ensure that these outcomes are similar in the two groups.*

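### Hypotheses 2 and 3 claim similar MS efficacy and no excess of adverse events, but the protocol assigns them only tests of difference, with no margin or interval criterion and by its own account little power

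*Protocol*

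**What the plan says.** Protocol section 2.b (Hypotheses) opens its list of four with "The following hypotheses will be tested". Hypothesis 2 is that consecutive alemtuzumab and rituximab "is associated with similar efficacy in MS disease control when compared to the administration of alemtuzumab with placebo". Hypothesis 3 is that the combination is safe, explained as "adverse events will be no more common than when alemtuzumab is administered with placebo".

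The section on data analysis and statistical considerations (section 3) gives the methods:

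- Adverse events other than the primary outcome "will be compared using frequencies and chi-squared statistics".
- Relapse and sustained disability progression are analysed with Cox models.
- Change in EDSS and new MRI lesions "will be assessed using linear regression analysis provided assumptions are met", with non-parametric methods as the alternative.

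The same section says that power to find significant differences in other adverse events or MS outcomes is unlikely to be sufficient. It continues: "these will be looked at carefully to ensure that these outcomes are similar in the two groups". The only success rule is for the primary outcome, a significantly lower hazard of autoimmune events on rituximab.

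**The concern.** Hypothesis 2 is an equivalence-type claim and hypothesis 3 is a claim of no excess. Each assigned method has no difference as its null hypothesis. Failing to reject that null does not establish it, least of all in a study that expects to lack power. To support either hypothesis, the plan would need a margin, or some rule about where a confidence limit must fall. Neither is stated.

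Safety of consecutive administration is the question the synopsis names under ethical and safety considerations, and the synopsis makes immediate adoption conditional on the strategy proving safe as well as effective. The section on risk mitigation recognises that the two drugs might add to each other's infection risk. An increase in infections is therefore the harm readers will most want the trial to describe accurately.

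**Working it through.** **1. The protocol's own figure.** The only sample size statement (Statistical power calculation) concerns the primary outcome: 80 participants, 40 per arm, 80% power, p < 0.05, 40% versus 10%. The usual two-proportion formula, two-sided 0.05, gives

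n = [1.96·√(2·0.25·0.75) + 0.842·√(0.4·0.6 + 0.1·0.9)]² / 0.30² = 31.5, so 32 per arm.

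With continuity correction it gives 38 per arm, close to the 40 stated. No power, sample size or margin is given for hypotheses 2 and 3.

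**2. Inputs for hypothesis 3.**

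- Arm sizes: 80 participants (Study Population) at 2:1 (Recruitment/Selection) give about 53 on rituximab and 27 on placebo, before any dropout.
- Two-sided 5% level. The protocol does not state sidedness, so this is an assumption.
- Placebo event rates: the protocol gives no general adverse event rate, so the rates below are assumptions shown as a range. The 7% row is the midpoint of the 6–8% HSV2 reactivation risk in the first month (Risk Mitigation Procedures). It is the only infection rate in the document and serves as illustration only.

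**3. Power of the chi-squared test to detect a doubling.** All 28 × 54 possible outcomes were enumerated. The binomial probabilities were summed over outcomes where the uncorrected chi-squared test gives p < 0.05.

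| Placebo rate | Rituximab rate | Power |
|---|---|---|
| 5% | 10% | 8% |
| 7% | 14% | 13% |
| 10% | 20% | 19% |
| 20% | 40% | 45% |
| 30% | 60% | 76% |
| 40% | 80% | 95% |

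At a 7% placebo rate, a true doubling would be non-significant about 87% of the time (100% − 13%).

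**4. Precision when the observed rates are equal.** The 95% half-width for a risk difference is 1.96·√[p(1−p)(1/53 + 1/27)], where 1/53 + 1/27 = 0.0559.

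- p = 10%: 1.96·√(0.09 × 0.0559) = 0.139, or 14 points.
- p = 30%: 21 points.
- p = 40% to 50%: 23 points.

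Identical observed rates of 10% would thus be compatible with an excess on rituximab of up to about 14 points.

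**5. No events at all.** Zero events among 53 on rituximab leaves a one-sided 95% upper limit of 1 − 0.05^(1/53) = 5.5%.

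**6. What a formal no-excess test would need.** The margins here are assumed, since the protocol has none. The setting is 2:1 allocation, one-sided 0.025, 80% power and equal true rates.

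| Event rate | Total N, 10-point margin | 15-point margin | 20-point margin |
|---|---|---|---|
| 7% | 231 | 105 | 60 |
| 20% | 567 | 252 | 144 |
| 40% | 849 | 378 | 213 |

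Of these nine cases, 80 participants suffice in only one: a 7% rate with a 20-point margin.

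**7. Hypothesis 2.** No arithmetic is possible, because the protocol gives no relapse or progression rate and no margin. The logic is the same: a Cox or regression coefficient that does not differ significantly from no effect does not demonstrate similar efficacy.

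**The case against.** The strongest reply is that the protocol is candid. It warns that power for these outcomes is probably inadequate, words its secondary objective as assessing safety and efficacy rather than demonstrating them, and attaches a success rule only to the primary outcome. Descriptive safety reporting is normal in phase II, frequencies are already planned, and the Cox models will yield hazard ratios. Much of this stands. It shows that the hypothesis wording and the promise to ensure similarity claim more than the rest of the document allows. It does not give either hypothesis a valid basis for a conclusion.

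A reader might infer that p > 0.05 will be reported as safety. The protocol does not say so; what it lacks is any criterion for accepting hypotheses 2 and 3. The synopsis wording about proving safe is a conditional remark on translation, not a decision rule tied to the chi-squared test.

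A reader might also infer that a doubled infection risk would usually be missed. That depends on the baseline rate. It holds for events with an assumed placebo rate of about 20% or less, not at 30% or 40%, and the protocol gives no overall infection rate.

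The choice of exact methods for sparse tables is secondary detail that an analysis plan may settle, and it is not part of this point.

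**Conclusion.** The point holds as an internal mismatch. Two hypotheses of similarity or no excess are declared to be tested, the methods assigned are tests of difference, and the same section concedes low power yet promises to ensure similarity. This comes from the protocol's own text and is not a gap left for an analysis plan.

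The size depends on assumed event rates and on 53 versus 27 participants without dropout. Power to detect a doubling is below 20% at placebo rates of 10% or less, and below one half at 20%. It is adequate only for very common events. Uncommon but important events, such as serious or specific infections, are where a non-significant result would say least. The primary analysis, its success rule and the sample size are not affected.

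**What to change.** - In section 2.b, restate hypotheses 2 and 3 as estimation objectives: to estimate the difference between arms in adverse events and in MS outcomes.
- In the data analysis section, make effect estimates with 95% confidence intervals the basis for interpretation, in place of chi-squared p-values. For adverse events, use risk differences or exposure-adjusted rate ratios. The section itself notes that follow-up is not uniform and uses a time-to-event model for the primary outcome for that reason. For MS outcomes, use hazard or rate ratios.
- State that safety or similarity will not be concluded from a non-significant result, and that the confidence limits describe how large an excess remains possible.
- Delete the clause about ensuring that the outcomes are similar.

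If the sponsor prefers to keep formal hypotheses, justified margins must be set in advance. As shown above, 80 participants would support only wide ones.

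The cost is changed wording in two sections and in the planned safety and efficacy summaries, and a more modest claim. Sample size, visits, treatment and the primary analysis stay as they are.

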## 3. Methods

### a. Methodological Approach

- *This will be a 3-year, multi-centre, double-blinded, randomised (2:1), placebo-controlled trial of rituximab versus placebo in pwMS being treated with alemtuzumab.*
- *Participants will be recruited from one of six hospitals across Queensland, Gold Coast University Hospital, Royal Brisbane and Women's Hospital, Mater Hospital Brisbane, Princess Alexandra Hospital, Sunshine Coast University Hospital and Townsville Hospital and Health Service.*
- *The study would aim to recruit patients over 24 months and follow individual participants for a minimum of 2 years.*

---

## b. Study Sites/Settings

- *This is a multi-centre study based in Queensland. The following clinical sites have been selected:*
  - *Gold Coast University Hospital*
  - *Royal Brisbane and Women's Hospital*
  - *Mater Hospital Brisbane*
  - *Princess Alexandra Hospital*
  - *Sunshine Coast University Hospital*
  - *Townsville Hospital and Health Service*
- *Each of these sites runs a dedicated MS Clinic led by a neurologist with sub-specialist training, expertise and experience in the management of pwMS. The service at each site is very similar and all have experience in treating MS with anti-CD52 (alemtuzumab) and anti-CD20 (rituximab) therapies. There is no plan to compare outcomes between sites although the randomisation strategy will include stratification by site.*
- *All treatment, study visits and magnetic resonance imaging (MRI) will be conducted at the study sites. Blood tests will be conducted both at the study sites and private pathology facilities (QML).*
  -

## c. Study Population

- *The study will aim to recruit 80 pwMS who are due to commence treatment with alemtuzumab.*
- *Inclusion criteria*
  - *Aged 18 – 55 years (inclusive)*
  - *Diagnosed with relapsing remitting MS (RRMS) by a neurologist*
  - *Diagnosis of MS meeting 2017 McDonald criteria*
  - *Diagnosed with MS within the previous 10 years*
  - *Expanded disability status scale (EDSS) score < 5.0*
  - *English speaking or non-English speaking who can ensure external interpreter assistance (e.g. relative or friend) to attend all visits for the duration of the clinical trial.*
  - *Available to attend clinic visits*
  - *Willing to sign up for and comply with Bloodwatch monitoring program*
  - *Fully vaccinated against COVID-19 (2 standard doses plus booster)*
- *Exclusion criteria*
  - *Known or suspected prior autoimmune disease (other than MS)*
  - *Any other serious co-morbidity that in the view of the investigator would preclude participation in the study*
  - *Pregnant (if female)*
  - *Currently lactating (if female)*

- 
- Unwilling or unable to use appropriate contraception for the treatment phase of the study (2 years) – male or female
  - Recent or current history of major depression, bipolar disorder, psychosis or suicidality
  - Currently or recently taking any illicit substances (including any cannabis product)
  - Allergy to valaciclovir
  - Allergy to Bactrim, Trimethoprim or Sulphur based antibiotics

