## **h. Study Procedure**

- *Treatment Arms*
- *Arm 1: Intervention*
- *Arm 2: Placebo*
- *Intervention Description, Dosage and Route of Administration*
- *The investigational product is rituximab, which is a monoclonal antibody against CD20 that cause lysis of B-lymphocytes. The antibody is a humanised mouse antibody and is administered intravenously via an infusion over a period of time that varies according to the dosage (see below). The dosage to be used is 100 mg/m^2 of estimated body surface area (BSA). BSA will be estimated based on height (H) and weight (W) according to the Du Bois formula:*
- *BSA = 0.007184 x W0.425 x H0.725*
- *With height measured in cm and weight measured in kg.*
- *Dosage will be rounded down to the nearest 10 mg.*
- *Study drug will be provided as a solution of 100 mg in 10 ml vials.*
- *Infusions will be delivered at set times of 10 weeks and 30 weeks after administration of alemtuzumab in combination with 100 mg intravenous methylprednisolone to reduce the risk of infusion reactions.*
- *Placebo*

- *Placebo will be 0.9% sodium chloride, which as a colourless solution is indistinguishable from diluted rituximab.*
- *Pre-medication*
- *Prior to administration of the study drug/placebo all trial participants (intervention and placebo arms) will be administered loratadine 10 mg orally and 100 mg intravenous methylprednisolone made up in 100 ml 0.9% sodium chloride and infused over 30 minutes.*
- *Preparation and Administration of Study Drug/Placebo*
- *Study drug and placebo will be made up by non-blinded onsite pharmacists according to the randomisation schedule product information sheet for rituximab. Specifically, the calculated dose of study drug will be aseptically withdrawn from vials and diluted in 100 ml of 0.9% sodium chloride ensuring that the calculated concentration is between 1 mg/ml and 4 mg/ml. To ensure adequate mixing the bag of diluted study drug/placebo will be gently inverted to avoid foaming. The prepared drug products will be visually inspected for particulate matter or discolouration.*
- *Rituximab/placebo will be administered according to Tables 1 and 2 below:*

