  - *At the conclusion of the trial, the Principal Investigator or nominee will perform a final inventory. If any supplies cannot be accounted for, this will be documented on the product accountability form together with an explanation of the discrepancy. The originals of the product accountability and dispensing logs must be sent to the trial coordinator. The Principal Investigator will retain copies of these logs on file.*
  - *Retention of Samples*
  - *The Principal Investigator or delegate will maintain accurate records demonstrating dates and amount of product received, to whom dispensed and accounts of any product accidentally or deliberately destroyed. It will be the responsibility of the Principal Investigator or delegate to ensure that adequate samples of all trial doses are retained in accordance with the relevant regulatory guidelines. For example, for trials conducted under the CTN scheme in Australia, at least a sample from each batch of product used in the trial should be retained for one year longer than the shelf-life of the product, and to comply with ICH-GCP requirements, sufficient quantities of the product(s)*

---

*should be retained either until the analyses of the trial data are complete or as required by the applicable regulatory requirements, whichever represents the longer retention period.*

- *Study Procedures and Visits*
- *Participants will be required to undergo the following study procedures and visits.*
- *Screening Visit (-30 - -7 days)*
  - *Informed consent will be obtained*
  - *Completion of eligibility criteria checklist*
  - *Comprehensive review of medical history including; details of MS history, other past medical and surgical history, past and current medications, family history, social history and allergies*
  - *Comprehensive medical and neurological examination*
  - *EDSS*
  - *HADS*
  - *Baseline/enrolment Visit (-7 - -4 days)*
  - *Informed consent will be re-obtained*
  - *Review of neurological symptoms*
  - *Review of medications*
  - *EDSS*
  - *MSIS29*
  - *Blood tests – FBC, EUC, LFT, TFT, Lymphocyte subsets, bHCG (in women)*
  - *Urine screen – red cell count and albumin*
  - *UACR*
- *Alemtuzumab therapy visits (Year 1, Day 1 – 5; Year 2, Day 1-3) – part of normal care*
  - *Loratidine 10 PO od (continued for 10 days)*
  - *Valaciclovir 500 mg PO od*
  - *Bactrim DS (960 mg) PO 3 times per week (Mon, Weds, Fri)*
  - *0.9% Sodium Chloride IV 1L over 8 hours*

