  - *Methylprednisolone 500 mg IV over 30 minutes*
  - *Alemtuzumab 12 mg IV over 4 hours*
  - *Hourly temperature, pulse and blood pressure*
  - *First month (Day 6 – 30) – part of normal care*
  - *Valaciclovir 500 mg PO od*
  - *Bactrim DS (960 mg) PO 3 times per week (Mon, Weds, Fri)*
  - *Bloodwatch pathology tests (Every month) – part of normal care*
  - *FBC/lymphocyte subsets (4 ml) – lymphocyte subsets will be performed at weeks -1, 4, 9, 13, 26, 35, 50, 57, 61, 65, 78, 83 and 104.*
  - *EUC/LFTs (10 ml)*
  - *Urine red cell count*

[figure not shown]
- *Urine albumin*
- *UACR*
- *TSH (every 3rd month)*
- *Intervention visits (At weeks 10 and 30 provided B-cell count >30% of pre-treatment level.*
  - *Loratidine 10 mg PO 30 minutes prior to rituximab.*
  - *Methylprednisolone 100 mg IV over 30 minutes, commencing 30 minutes prior to rituximab.*
  - *Rituximab 100 mg per m^2 or placebo IV over 1 hour*
- *Monitoring visits (Every 6 months – weeks 25, 51, 77, 103, 129)*
  - *Review of relapse history*
  - *Review of adverse events*
  - *Review of intercurrent illness*
  - *Review of concomitant medications*
  - *EDSS*
  - *Monitoring visits may be conducted remotely via telehealth whether for reasons of COVID-lockdowns or remoteness of the participant*
- *MRI (Every 12 months – Baseline, Weeks 51, 103, 155)*
  - *MRI Brain*
  - *Closeout visit (Week 155 or earlier at close of study)*
  - *Review of relapse history*
  - *Review of adverse events*
  - *Review of intercurrent illness*
  - *Review of concomitant medications*
  - *EDSS*
  - *MSIS-29*
- *The timeline of participant involvement and total time commitment per patient in the trial is outlined in Table 3. Participants will also undergo the following procedures as part of normal care for someone receiving alemtuzumab. Admissions to day infusion centre for 8 hours on 5 days in year 1 and 3 days in year 2 for administration of alemtuzumab. They will also undergo monthly blood and urine tests as listed about through any private pathology firm convenient to them as part of the Bloodwatch® (RxMx®, Australia) monitoring program. The additional lymphocyte subset counts will be undertaken as part of the same blood draw and will not involve any additional tubes or time.*
- *Time constraint tolerance on study related procedures will be as follows:*
- *Screening visit, Enrolment, Review visit, EDSS and Screening bloods will be +/- 1 week.*

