## **i. Outcome Measures**

- *Primary outcome measure: the frequency of autoimmune adverse events (autoimmune thyroid disease, idiopathic thrombocytopenia, anti-GBM renal disease and any other autoimmune diseases).*
- *Secondary outcome measures:*
  - *Other adverse events, in particular infections*
  - *Measures of alemtuzumab treatment efficacy*
    - *Time to first relapse or new disease activity on MRI*
    - *Time to first relapse*
    - *Annualised relapse rate*
    - *EDSS*
    - *MSIS-29*
    - *Sustained disability progression*
    - *Number of new T2 lesions on MRI*
    - *Number of new Gd-enhancing lesions on MRI*
  - *Measure of lymphocyte reconstitution*
    - *Total lymphocyte count*
    - *CD4, CD8, CD20 counts*
    - *B-cell subpopulation counts.*

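### CD20, the target of the study drug, is the named B-cell marker, which may bias hypothesis 4 soon after infusion; separately, entry soon after anti-CD20 therapy is allowed and may dilute the primary contrast

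*Protocol*

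**What the plan says.** **Eligibility.** Protocol section 3.c states: "The study will aim to recruit 80 pwMS who are due to commence treatment with alemtuzumab". Disease history is bounded by "Diagnosed with MS within the previous 10 years". The exclusions cover other autoimmune disease, co-morbidity, pregnancy and lactation, contraception, psychiatric history, illicit substances and drug allergies. None concerns earlier MS treatment, and no washout is set. Section 3.b says of the six sites that "all have experience in treating MS with anti-CD52 (alemtuzumab) and anti-CD20 (rituximab) therapies". The screening visit in section 3.h records "past and current medications", but no criterion uses that record.

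**Marker.** Section 3.h states: "The investigational product is rituximab, which is a monoclonal antibody against CD20". Section 3.i lists "CD4, CD8, CD20 counts" among the measures of lymphocyte reconstitution, and separately the B-cell subpopulations, for which no marker is given. Hypothesis 4 (section 2.b) compares early B-cell return between the arms.

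**30% criterion.** Section 3.h schedules the infusion visits "provided B-cell count >30% of pre-treatment level", and section 3.f says the same in other words. Neither names a marker. The reference is the participant's own pre-treatment count, and only one such count is scheduled, at week -1.

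**The concern.** The two matters share a theme but touch different analyses.

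(a) A count that relies on CD20 can read low because the cells are gone or because the study drug occupies the marker. The second mechanism can act only where rituximab was given. It would therefore be a measurement difference between the arms, on the very outcome that hypothesis 4 compares.

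(b) Anti-CD20 depletion is the experimental exposure. A person who comes to alemtuzumab soon after such a drug and is allocated to placebo may carry part of that exposure into the control arm. A person with the same history allocated to rituximab receives the exposure anyway. The expected consequence is a smaller difference in the primary outcome. For the same person, a depleted week -1 count becomes the reference for the 30% criterion, so passing it no longer shows that B-cells have returned.

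**Working it through.** **(a) Timing of counts against infusions**

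Inputs: infusions at weeks 10, 30, 62 and 82 (Table 3); subset counts at weeks -1, 4, 9, 13, 26, 35, 50, 57, 61, 65, 78, 83 and 104 (section 3.h). The documents give no half-life, so 2 to 4 weeks is assumed. Share of the latest infusion remaining = 0.5^(gap / half-life).

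| Count (week) | Weeks since latest infusion | Remaining, half-life 2 to 4 weeks |
|---|---|---|
| 13 and 65 | 3 | 35% to 59% |
| 35 | 5 | 18% to 42% |
| 83 | 1 | 71% to 84% |
| 26 and 78 | 16 | 0.4% to 6% |
| 50 | 20 | 0.1% to 3% |
| 57 | 27 | below 1% |
| 61 | 31 | below 1% |
| 104 | 22 | below 0.1% to 2% |

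Weeks 4 and 9 precede any study drug. Of the ten counts after the first infusion, four are exposed and six are nearly clear. These figures are residual drug, not bias in the count; the documents do not allow the bias to be sized.

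**(b) Effect on the primary contrast**

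The plan's own figure comes first. The power statement gives 80% power at p < 0.05 for 40% versus 10% with 40 per arm. With the two-sided pooled formula,

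power = Φ{ [d − 1.96·√(p̄(1−p̄)(1/n₁+1/n₂))] / √(p₁(1−p₁)/n₁ + p₂(1−p₂)/n₂) }.

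- At 40/40, d = 0.30 and p̄ = 0.25: (0.300 − 0.190)/0.0908 = 1.21, so power is 88.8%. It is 82.6% with continuity correction and 85.2% by Fisher's exact test. The stated 80% is therefore conservative.
- At the 2:1 split of section 3.a, about 27 placebo and 53 rituximab, p̄ = (10.8 + 5.3)/80 = 0.201: (0.300 − 0.186)/0.103 = 1.11, so power is 86.6%.

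Now let a share f of controls have carry-over, with event rate r. The control rate is 0.40(1−f) + r·f, and the rituximab arm stays at 10%. Both f and r are assumptions. r = 10% is full protection (a ceiling); r = 25% is half.

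| f | Control rate, full | Power at 27/53, full | Control rate, half | Power at 27/53, half |
|---|---|---|---|---|
| 0% | 40% | 86.6% | 40% | 86.6% |
| 10% | 37% | 80.6% | 38.5% | 83.8% |
| 20% | 34% | 73.1% | 37% | 80.6% |
| 30% | 31% | 64.2% | 35.5% | 77.0% |

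Fisher's exact test at 27/53 gives 85.2%, 78.3%, 69.6% and 59.4% down the full-protection column. The planned analysis is a Cox model, so the two-proportion results stand in for it. Each affected control is 1/27, or 3.7%, of that arm.

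**30% reference.** A participant whose week -1 count is 50%, 20% or 10% of their undepleted level passes at 0.30 × 50% = 15%, 0.30 × 20% = 6% or 0.30 × 10% = 3% of that level.

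**The case against.** On (a), the documents nowhere say that bound rituximab hides CD20. Section 3.h says the drug lyses B-cells, so a low count after infusion is expected in any case. Six later counts are almost free of drug, and CD20 is tied to one line of a secondary list. This largely stands. A reader might infer that depletion and masking cannot be told apart at all, or that masking corrupts the 30% criterion. Neither follows. The later counts allow the separation. The last scheduled counts before each infusion (weeks 9, 26, 61 and 78) either precede study drug or have at most about 6% of the latest infusion remaining, and that criterion names no marker. What survives is that masking follows plausibly from the stated target, would act in one arm only, and affects four of the ten relevant counts.

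On (b), nothing shows that anyone will switch from anti-CD20 therapy; section 3.b records site experience only. Randomisation spreads prior users over both arms in expectation. Full protection from one exposure before baseline, set against four infusions timed around two alemtuzumab courses, is generous. Even so, power stays near the planned 80% with 10% of controls affected. All of this stands and limits the size. A reader might infer that carry-over does reach the control arm, or that it could create a false benefit. The first is possible but not shown; the second is not the expected direction, although chance imbalance can occur with about 27 controls.

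A sensitivity analysis by prior therapy could properly sit in the statistical analysis plan. Eligibility and the named outcome marker are fixed in the protocol.

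**Conclusion.** Both matters hold in limited form.

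(a) As written, the hypothesis 4 comparison is open to measurement bias in one arm at weeks 13, 35, 65 and 83 and may overstate suppression there. The size is unknown. The conclusion rests on the stated drug target and on an assumed half-life of 2 to 4 weeks. Suppression judged from the counts 16 or more weeks after infusion is little affected.

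(b) Entry soon after anti-CD20 therapy is permitted. If it happens, the likely effect is dilution toward no difference: about 3 to 6 points of power with 10% of controls affected and 6 to 13.5 points with 20%, from half to full protection. It would also leave the 30% reference uninformative for those participants. The share affected and the degree of protection are both assumptions.

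**What to change.** (a) In section 3.i, replace CD20 with CD19 as the B-cell count used for hypothesis 4. It is a change of marker in the same subset test with no extra blood, since section 3.h already takes these counts from the routine draw. The 30% criterion in sections 3.f and 3.h names no marker; the sponsor should reconcile those sections with the outcome list. No dosing rule is proposed here.

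(b) In section 3.c, add an exclusion for anti-CD20 therapy within a washout that the sponsor defines. It can be checked from the medication history already taken at screening; the cost is a few fewer eligible patients. An exclusion based on a low B-cell count would fit poorly, because the pre-treatment subsets are drawn at the enrolment visit, where randomisation takes place.
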